5.9 Pharmacokinetic, Pharmacodynamic, and Biomarker Analysis

5.9.1 Pharmacokinetic Analyses

The PK of the antibody-drug conjugate (brentuximab vedotin), total antibody, and unconjugated drug (MMAE) will be based on serum or plasma samples collected from patients who meet study inclusion criteria, received study drug, and provided evaluable PK data. Population PK parameters will be calculated with an appropriate method based on a validated PK analysis program. Exploratory safety-PK, efficacy-PK, and if possible, PK-pharmacodynamic relationships will be determined.

**Brentuximab vedotin (ADCETRIS™)
Statistical Analysis Plan, Study C25003**

Descriptive statistics (eg, number of patients, mean, standard deviation, median, minimum, and maximum) will be used to summarize concentrations of analyte for brentuximab vedotin-treated patients.

The pharmacokinetics of doxorubicin, vinblastine, and dacarbazine will be compared between the treatment arms. Descriptive statistics (eg, number of patients, mean, standard deviation, median, minimum, and maximum) will be used to summarize concentrations of analyte. Geometric mean ratios of the AUC will be calculated for each AVD component (doxorubicin, vinblastine, and dacarbazine).

5.9.2 Immunogenicity Analysis

All patients who were administered at least 1 dose of brentuximab vedotin will be evaluated for antitherapeutic antibody (ATA) development. A list/table of ATA status will be provided. Antibody neutralizing status (neutralizing or not neutralizing) will also be listed for patients who have positive antibody status.

Immunogenicity information, including ATA and neutralizing ATA, will be summarized in descriptive statistics as applicable.

Relationships between ATA development and safety and efficacy will be explored.

5.9.3 Biomarker Analysis

Absolute and change from baseline value of circulating biomarkers will be summarized by time point using descriptive statistics, as applicable. Descriptive statistics (eg, number of patients, mean, standard deviation, median, minimum, and maximum) will also be provided to summarize disease markers (CCI [REDACTED]), tissue levels of potential resistance markers (CCI [REDACTED]), and qualitative and semiquantitative measures of markers (CCI [REDACTED]), and change from baseline values of these markers, as applicable. The association between these and clinical response or safety endpoints might be explored.

5.10 Resource Utilization and Patient-Reported Outcome Analysis

Analyses of patient-reported outcomes (PROs) and health economics will be performed using the ITT population.

5.10.1 Patient-Reported Outcomes Analysis

Patient-reported outcome (PRO) assessments based on EORTC QLQ-C30, FACIT Dyspnea 10, and FACT/GOG-NTX Additional scale will be analyzed to determine if response to therapy is accompanied by changes in the quality of life.

The analysis will be based on scores from the global health status/QoL scale of QLQ-C30, shortness of breath scale of FACIT Dyspnea 10, and the sensory scale of FACT/GOG-NTX. The analysis of change of scores from baseline will use mixed-effects models with repeated measures at each time point specified in the Schedule of Events of the protocol and the 95% CIs of the estimates will be provided.

Descriptive summaries of all the scales and individual item scores observed will be generated at each scheduled assessment time point by treatment.

Missing data will be summarized with the proportion of missing responses for each item over time. Manuals for scoring and handling missing data published for QLQ-C30, FACIT Dyspnea 10, and FACT/GOG-NTX will be used to impute missing data initially.

A sensitivity analysis will be performed to evaluate the impact on the analysis results from missing data imputation. Conditional on the patterns of missing data, multiple imputation methods, including a pattern-mixture model, will be considered. Any deaths that occur before the end of treatment (EOT) are to be imputed by a value zero and will be considered missing otherwise.

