- g. All questionnaires should be completed on screening, Day 1 of every cycle (before any other study procedures are performed), 30 days after last dose of Frontline Therapy, and during posttreatment follow-up unless indicated otherwise (see table below). If screening questionnaires were completed within 4 days before Cycle 1 Day 1, they do not need to be repeated on Cycle 1 Day 1. Patient-reported outcomes will be evaluated using the European Organization for Research and Treatment of Cancer (EORTC) QLQ-C30, the FACIT-Dyspnea 10 questionnaire, the EQ-5D questionnaire, and the Functional Assessment of Cancer Therapy—Neurotoxicity (FACT-Ntx; Abbreviated).

Patient Reported Outcomes	End of Collection Period
FACIT-Dyspnea 10 Item Short Form	Collected until EOT
FACT-Ntx Abbreviated	Collected until EOT
EuroQOL EQ-5D (Utility Measurement)	Collected until 3 years post last dose of frontline therapy or development of confirmed progressive disease (PD), whichever occurs first
EORTC QLQ-C30	Collected at all patient visits (as outlined in the SOE table), including visits during the PTFU, until the final visit by the patient

- h. Includes serious pretreatment events. Serious pretreatment events will be reported to Millennium Department of Pharmacovigilance & Risk Management or designee from the time of signing ICF up to first dose of study drug, but will not be recorded in the eCRF.

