#### **7.4.15 Utility Measurement**

The EuroQOL EQ-5D is a 5-item questionnaire with a “thermometer” visual analog scale ranging from 0 (worst imaginable health state) to 100 (best imaginable health state) that will be administered as specified in the [Schedule of Events](#). The utility measurement should be collected until the sooner of development of confirmed PD or 3 years after the last dose of frontline therapy.

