### **8.1.7.1 Patient-Reported Outcomes Analysis**

PRO assessments based on the QLQ-C30 will be analyzed to determine if treatments affect PRO scores. Analyses of PRO scores including global health status will be performed using longitudinal models. All subscales and individual item scores will be tabulated. Descriptive summaries of observed data will be provided at each scheduled assessment time point. PRO assessments based on FACIT Dyspnea 10 and FACT-Ntx Abbreviated; will be analyzed using the same methods as QLQ-C30.

Initially, the manuals for scoring and handling missing data published for QLQ-C30, FACIT Dyspnea 10, and FACT-Ntx Abbreviated; will be used. Further investigation of missing patterns and details of imputation will be discussed in SAP.

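### SAP 5.10.1 imputes one fixed value, zero, for deaths before EOT on all three modelled PRO scales, whatever their scoring direction

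*SAP*

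**What the plan says.** SAP 5.10.1 models three scales: the "global health status/QoL scale of QLQ-C30", then the "shortness of breath scale of FACIT Dyspnea 10, and the sensory scale of FACT/GOG-NTX". The method is given as "The analysis of change of scores from baseline will use mixed-effects models with repeated measures". Missing data are first handled by the published scoring manuals.

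The next paragraph opens with "A sensitivity analysis will be performed to evaluate the impact on the analysis results from missing data imputation", mentions multiple imputation and pattern-mixture models, and ends with the death rule: "Any deaths that occur before the end of treatment (EOT) are to be imputed by a value zero and will be considered missing otherwise". The rule names no scale, makes no exception and does not mention scoring direction.

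No other text corrects it. Protocol 8.1.7.1 defers to the SAP: "Further investigation of missing patterns and details of imputation will be discussed in SAP". SAP 5.4.1 makes no imputation the default unless something else is specified, so the sentence in 5.10.1 is the only rule in either document for a PRO value after death.

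The table under footnote g of the protocol's Schedule of Events lists both FACIT-Dyspnea 10 and FACT-Ntx as "Collected until EOT". For these two instruments the rule therefore spans the whole collection period.

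**The concern.** One of the three scales is named for well-being and another for a symptom. A single number is the bad end of both only if they happen to be scored the same way. If the shortness-of-breath score counts severity, zero is its good end, and a patient who dies during treatment enters the data as free of breathlessness.

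The rule is also open on two further points. The modelled variable is change from baseline, and the SAP does not say whether zero is the score or the change. Nor does it say whether the rule feeds the main mixed model or only the sensitivity analysis. Two programmers could implement it differently and both claim to follow the SAP.

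At stake is the reading of the dyspnea scale. Lung-specific PROs are an exploratory objective (protocol 2.3), in a trial whose rationale includes removing the pulmonary risk of bleomycin (protocol 1.4).

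**Working it through.** The documents give no sample size, power or effect size for any PRO, so there is no planned figure to reproduce. The check is first logical, then an illustration of size.

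**What a death receives under each reading**

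- Zero is the score, and zero is the bad end of the scale: death gets the worst score, as presumably intended.
- Zero is the score, and higher means more symptoms: death gets the best score.
- Zero is the change from baseline: death counts as no change, on all three scales and in either direction.

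Only the first case gives a worst-outcome imputation, and it must hold for all three scales at once. Neither document states their direction. The only zero anchor given is for the EQ-5D visual analogue scale (protocol 7.4.15, zero worst). That instrument is handled in SAP 5.10.2 and cannot settle the matter.

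**One patient.** Assume a 0-100 symptom scale, higher worse, with zero as the score. For baseline b, the change is 0 − b with zero imputed and 100 − b with the worst score.

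- b = 20: −20 against +80
- b = 40: −40 against +60
- b = 60: −60 against +40

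With zero, the death counts as the largest improvement that patient could show.

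**One arm.** Let d be the share of deaths before EOT and m the mean among survivors. The shift in the arm mean at EOT is −m·d with zero and (100 − m)·d with the worst score, so the gap is 100·d whatever m is. With m = 30 (assumed):

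- d = 1%: −0.3 against +0.7, gap 1 point
- d = 3%: −0.9 against +2.1, gap 3 points

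**How many early deaths the plan implies.** Inputs: 5-year OS of 91% (A+AVD) and 88% (ABVD) from protocol 8.1.6.2; 620 patients per arm from protocol 4.2; last dose on Cycle 6 Day 15 and EOT 30 days later from the Schedule of Events. Time to EOT is (5 × 28 + 15 − 1 + 30) / 365.25 = 184 / 365.25 = 0.504 years. With a constant hazard (assumed), P(death before EOT) = 1 − S(5)^(0.504/5):

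- A+AVD: 1 − 0.91^0.1008 = 0.95%, or 5.9 of 620
- ABVD: 1 − 0.88^0.1008 = 1.28%, or 7.9 of 620

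The one-arm gap is then about 1.0 and 1.3 points respectively.

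**Between arms.** The rule applies to both arms, so what counts is the difference in death shares: 1.28% − 0.95% = 0.33 percentage points.

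- Bias in the arm difference from zero: 30 × 0.0033 = about 0.1 point, in favour of the arm with more deaths
- Movement in the arm difference on switching from zero to the worst score: 100 × 0.0033 = about 0.3 point

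A larger imbalance scales directly: 3% deaths in one arm and 1% in the other would give 100 × 0.02 = 2 points.

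**The case against.** The strongest reply is that the harm depends on a fact outside the documents. Both refer to the scoring manuals, and if all three modelled scores have zero at the bad end, a score of zero is already the worst value. That stands: the best-outcome consequence is conditional. It does not rescue the wording, which leaves the result to a direction the SAP never states and fails in any case if zero means change.

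The rule's position also matters. It stands with the sensitivity analysis, and its natural reading may be limited to that. This stands too, and is why the fix must say where the rule applies.

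Three stronger readings are tempting but not supported.

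- A reader might infer that every PRO is affected. Only three scales are modelled. The remaining scales and items get descriptive summaries of observed scores, and EQ-5D is in SAP 5.10.2.
- A reader might infer that a fatal lung event would improve the dyspnea result of its arm. That needs the unverified direction, zero as a score, and use of the rule in the main model. Nor would such deaths be hidden: SAP 5.11.1.3 summarises all deaths with cause, and OS is the key secondary endpoint.
- A reader might take 1-3 points as the treatment-comparison error. That is a one-arm figure; the between-arm figure is about ten times smaller at the low end under the protocol's own survival assumptions.

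Finally, worst-score imputation is one convention among several. While-alive or composite approaches are legitimate alternatives.

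**Conclusion.** The point holds as a minor defect in a stated rule. A single zero for deaths before EOT is safe on all three modelled scales only if all have zero as the worst score and zero means the score. The SAP establishes neither condition.

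The numerical consequence is small: about 0.1 point of bias in the arm difference, and about 0.3 point of movement on switching to the worst score. These figures rest on a 0-100 scale with higher worse, a survivor mean of 30 for the bias figure, every patient contributing a value at EOT, and a constant hazard through the protocol's 5-year OS rates. They grow only with an imbalance in early deaths.

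The QLQ-C30 is a secondary endpoint, and FACIT-Dyspnea 10 and FACT-Ntx are exploratory (protocol 3.2 and 3.3). mPFS and OS are untouched.

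**What to change.** In SAP 5.10.1, replace the fixed zero with the worst possible score of the respective scale per its scoring manual, with change from baseline computed from that score. Add one sentence saying whether the rule applies to the main mixed model or only to the sensitivity analysis.

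The wording is correct in either scoring direction and changes nothing where a score of zero is already the worst. If zero was meant as a change, it does alter the rule on all three scales, and the sponsor should make that choice knowingly.

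The cost is a little extra programming. The dyspnea result may also look slightly less favourable in the arm with more early deaths.

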5.10.2 Health Economics Analysis Using Medical Resource Utilization and Utility

EQ-5D scores will be summarized in descriptive statistics for treatment arms.

MRU data will be summarized in descriptive statistics of medical encounters (length of stay, inpatient, outpatient, and reason), number of missing days from work or other activities by patient and care-giver for treatment arms.

Further modeling will be performed separately at post hoc analyses.

5.11 Safety Analyses

Safety will be evaluated by the incidence of TEAEs, severity and type of AEs, and by changes from baseline in the patient's vital signs, ECOG performance status, ECG, and

**Brentuximab vedotin (ADCETRIS™)
Statistical Analysis Plan, Study C25003**

clinical laboratory results. Exposure to study drug and reasons for discontinuation will be tabulated.

These analyses will be performed using the safety population.

5.11.1 Adverse Events

Treatment-emergent adverse events are defined as any AE that occurs after administration of the first dose of study drug and through 30 days after the last dose of frontline therapy.

The MedDRA dictionary will be used to code the investigator's adverse event terms.

Adverse event tables will summarize subject incidence by treatment group actually received.

The severity of adverse events will be assessed using NCI CTCAE version 4.03.

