**Brentuximab vedotin (ADCETRIS®)****Clinical Study Protocol C25003 Amendment 7, EudraCT: 2011-005450-60**

performed every 3 months during the first year of posttreatment disease follow-up, then every 6 months until study closure (5 years after the last patient is enrolled). If, for any reason other than death or documented disease progression, a patient discontinues randomization therapy (A+AVD or ABVD) after Cycle 2 Day 25 but before completion of randomization therapy, every effort must be made to obtain PET and CT scans prior to initiation of subsequent therapy for HL. Responses and relapses will be assessed by an IRF. Evaluations will be performed until progressive disease (PD) is documented, receipt of second-line anticancer therapy for HL (including chemotherapy or radiation), death occurs, or the end of study. Patients will be followed for survival until death or for a minimum of 5 years after enrollment of the last patient.

Deauville scoring (see Section 15.6) per IRF will be used to evaluate the results of patients' Cycle 2 Day 25 PET/CT. Patients whose disease earns a Deauville score of 4 or less will continue study drug treatment according to their randomized arm (ABVD or A+AVD). Patients whose PET-positive disease earns a score of 5 may, at the investigator's discretion, receive an alternative regimen (physician's choice) for the remainder of planned frontline therapy. Patients with a Deauville score of 5 who, at investigator's discretion, are taken off study drug will be continue to be followed for response assessment; switching therapy prior to completion of frontline therapy will not be considered an mPFS progression event. Of further note, any switch in therapy prior to completion of frontline therapy will not be considered an mPFS event.

An interim futility analysis will be conducted when the first approximately 348 patients have completed the regimen to which they were randomized (ie, received the planned study drug regimen with no more than 2 missed doses of A+AVD or ABVD) or have discontinued treatment prior to completion. The final analysis of the mPFS primary endpoint will be conducted when 260 mPFS events occur; an interim analysis of OS will also be conducted at that time. The final analysis of OS will be conducted when 112 deaths occur, approximately 4 years after randomization of the last patient.

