**Table 8-1 Completion of Frontline Therapy**

Treatment History	Completion of Frontline Therapy
Did not switch therapy	Upon receipt of planned study drug regimen with no more than 2 missed doses of A+AVD or ABVD a
Switched therapy before completion of A+AVD or ABVD	Upon conclusion of 1 alternative anticancer regimen b for HL subsequent to A+AVD or ABVD discontinuation

a A "missed dose" refers to administration of the full study regimen of either A+AVD or ABVD. Patients may miss individual agents within the A+AVD or ABVD regimen (such as patients who discontinue bleomycin for pulmonary toxicity) without this counting as a missed dose.

b Receipt of chemotherapy OR radiation.

Patients without a documented mPFS event at the time of analysis (defined as PD/relapse, subsequent anticancer therapy for residual disease after completion of planned frontline therapy for HL, or death) will be censored at the date of last response assessment. Detailed handling rules for missing assessments and censoring for the analysis of mPFS will be described in Section 5.8.1.2 of the SAP.

Modified PFS will be tested at a 1-sided 0.025 level at the final analysis.

In addition, a stratified Cox regression model will be used to estimate the hazard ratio and the 95% CI for the treatment effect. The Kaplan-Meier survival curves, 25th, 50th (median), and 75th percentiles (if estimable), along with their 2-sided 95% CIs, will also be presented for each treatment arm.

Sensitivity analyses for mPFS per IRF will be performed using the PP population. Modified PFS per IRF using different censoring approaches will be also analyzed in the ITT population. Details of different censoring approaches and further sensitivity analyses of

mPFS will be included in the SAP. Modified PFS per investigator will also be analyzed similarly using the ITT population.

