#### **8.1.9 Safety Analysis**

Safety will be evaluated by the incidence of AEs, severity and type of AEs, and by changes from baseline in the patient's vital signs, weight, and clinical laboratory results using the safety population. Exposure to frontline therapy and reasons for discontinuation will be tabulated.

Treatment-emergent AEs that occur after administration of the first dose of study drug and through 30 days after the last dose of frontline therapy will be tabulated.

AEs will be tabulated according to the Medical Dictionary for Regulatory Activities (MedDRA) and will include the following categories:

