1.2 Study Objectives

Primary Objective:

- To compare the modified progression-free survival (mPFS) obtained with brentuximab vedotin plus AVD (abbreviated A+AVD) versus that obtained with ABVD for the frontline treatment of advanced classical HL

Key secondary objective:

- To determine if A+AVD improves overall survival (OS) versus that obtained with ABVD

Other secondary objectives:

- To determine if A+AVD improves complete remission (CR) rate at the end of randomized regimen versus that obtained with ABVD
- To determine the safety profile of A+AVD relative to that of ABVD
- To determine the event-free survival (EFS) obtained with A+AVD and ABVD
- To determine the disease-free survival (DFS) obtained with A+AVD and ABVD
- To determine if A+AVD improves overall objective response rate (ORR, defined as CR + PR) versus that obtained with ABVD
- To determine the duration of response (DOR) and duration of complete response (DOCR) obtained in the A+AVD and ABVD arms
- To determine the rate of patients receiving irradiation for HL not in CR in the A+AVD and ABVD arms
- To determine the rate of patients in CR at the end of frontline therapy in the A+AVD and ABVD arms
- To determine the rate of Cycle 2 PET negativity in patients treated with A+AVD versus those treated with ABVD

**Brentuximab vedotin (ADCETRIS™)
Statistical Analysis Plan, Study C25003**

- To determine if A+AVD improves health-related quality of life (HRQoL) versus ABVD
- To describe the PK of brentuximab vedotin, MMAE, and total antibody (TAb) in blood
- To determine the immunogenicity of brentuximab vedotin

Exploratory objectives:

- To investigate any differences in lung-specific patient reported outcomes (PRO) between the treatment arms
- To assess any impact of brentuximab vedotin dosing on serum concentrations of AVD
- To investigate any differences between the treatment arms in the rate of patients alive without HL at 3 and 5 years
- To assess changes in tumor biomarker expression before and after treatment
- CCI [REDACTED]
[REDACTED]
[REDACTED]
- To assess other PROs
- To assess medical resource utilization
- To assess fertility

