5.7.2.2 Treatment Modifications

Action on each component of study treatments A+AVD and ABVD will be summarized by Cycles 1 through 6.

Patients who switch to another frontline therapy before completing A+AVD and ABVD will be summarized by time of switch and by treatment to which they switch.

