5.8.1.1 Definition

mPFS is defined as:

The time from the date of randomization to the date of the first of (1) documentation of progressive disease (PD); (2) death due to any cause; (3) for patients who are confirmed non-complete responders per IRF, receipt of anticancer chemotherapy or radiotherapy for HL after completion of frontline therapy, as defined in [Table 5-1](#); these patients' mPFS event date will be the date of the first PET scan post completion of frontline therapy demonstrating the absence of a CR, defined as a Deauville score of ≥ 3 .

Table 5-1 Completion of Frontline Therapy

Treatment History	Completion of Frontline Therapy
Did not switch therapy	Upon receipt of planned study drug regimen with no more than 2 missed doses of A+AVD or ABVD ^a
Switched therapy before completion of A+AVD or ABVD	Upon conclusion of 1 alternative anticancer regimen ^b for HL subsequent to A+AVD or ABVD discontinuation

a A "missed dose" refers to administration of the full study regimen of either A+AVD or ABVD. Patients may miss individual agents within the A+AVD or ABVD regimen (such as patients who discontinue bleomycin for pulmonary toxicity) without this counting as a missed dose.

b Receipt of chemotherapy OR radiation.

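### The all-cause adverse-event tables run through any alternative frontline regimen, so they describe a treatment strategy, while the stated safety objective compares A+AVD with ABVD

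*SAP*

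**What the plan says.** The SAP (5.11.1) defines a TEAE as "any AE that occurs after administration of the first dose of study drug and through 30 days after the last dose of frontline therapy". Protocol 8.1.9 has the same end point: events "through 30 days after the last dose of frontline therapy will be tabulated". Collection in Protocol 10.3 also follows frontline therapy.

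Frontline therapy is wider than the randomized regimen. Under Protocol 4.1, a patient with a Cycle 2 Deauville score of 5 may "receive an alternative regimen (physician's choice) for the remainder of planned frontline therapy". For anyone who switches before completing A+AVD or ABVD, Protocol Table 8-1 and SAP Table 5-1 place completion of frontline therapy "Upon conclusion of 1 alternative anticancer regimen", and a footnote explains that regimen as "Receipt of chemotherapy OR radiation". SAP 5.7.2.2 uses the same language: "Patients who switch to another frontline therapy before completing A+AVD and ABVD" are summarised by time of switch and by new treatment.

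The study treatments are A+AVD and ABVD only (SAP 5.7.2), and adverse-event tables are by treatment group actually received (SAP 5.11.1). The safety objective in SAP 1.2 is "To determine the safety profile of A+AVD relative to that of ABVD".

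**The concern.** Read together, these definitions put toxicity of the alternative regimen into the A+AVD or ABVD column. No safety table in SAP 5.11 stops at the switch, gives switchers their own column or separates post-switch events. Receipt of alternative frontline therapy is a subgroup for mPFS (SAP Table 5-4) but not for safety.

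Switching happens after randomization and, by the permitted route, depends on response, so its frequency may differ by arm. The physician's choice is not named and may be a more toxic regimen; Protocol 6 notes that expanded multi-agent regimens brought increased toxicity. One example shows what is at stake. Protocol 1.4 gives avoidance of bleomycin-associated lung toxicity as part of the rationale for A+AVD. The same section lists BEACOPP, which contains bleomycin, among the most commonly used frontline therapies. If an A+AVD patient were switched to such a regimen, its pulmonary events would appear under A+AVD.

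**Working it through.** The plan states no figure to reproduce on this point. The check has three parts.

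**1. Which tables are affected**

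| Output | Affected by the window? |
|---|---|
| All-cause TEAE, Grade 3 or higher and SAE incidence (SAP 5.11.1.1, 5.11.1.2) | Yes, fully |
| The same, related to study drug | In part; filtered by the investigator's causality judgement, with treatment known (Protocol 6.7, 10.2) |
| Deaths (SAP 5.11.1.3) | No; all deaths are included whatever their TEAE status |
| Exposure | Frontline therapy in Protocol 8.1.9; A+AVD and ABVD components in SAP 5.7.2.1; study drug in SAP 5.11 |

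**2. Length of the window for one switcher**

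Dosing is on Days 1 and 15 of 28-day cycles, for up to 6 cycles (SAP 1.1). Take a patient whose last study-drug dose is Cycle 2 Day 15. Assume the alternative runs to the planned Cycle 6 Day 15 date.

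- Cycle 2 Day 15 = 28 + 15 = day 43. A window tied to study drug closes on day 43 + 30 = 73.
- Cycle 6 Day 15 = 5 × 28 + 15 = day 155. The current window closes on day 155 + 30 = 185.
- Extra time: 185 − 73 = 112 days, or 112 / 185 = 61% of the window.

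The text sets no calendar limit, so a longer alternative extends the window further.

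**3. Effect on incidence**

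Let s be the proportion of an arm that switches and q the share of switchers whose first event of a given type falls after the switch. Patients count once per term (SAP 5.11.1.1), so the arm's incidence rises by s × q. The denominator is taken as the planned 620 per arm. Both s and q are assumptions.

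| s | Switchers (620 × s) | q = 20% | q = 50% | q = 80% |
|---|---|---|---|---|
| 1% | 6.2 | 0.2 points | 0.5 | 0.8 |
| 2% | 12.4 | 0.4 | 1.0 | 1.6 |
| 5% | 31.0 | 1.0 | 2.5 | 4.0 |
| 10% | 62.0 | 2.0 | 5.0 | 8.0 |

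The corners are 620 × 0.01 × 0.2 = 1.2 patients and 620 × 0.10 × 0.8 = 49.6 patients.

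The shift in the between-arm difference (ABVD minus A+AVD) is s(ABVD) × q(ABVD) − s(A+AVD) × q(A+AVD). Suppose 2% to 5% of A+AVD and 5% to 10% of ABVD patients switch, with q between 30% and 50%:

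- A+AVD: 0.02 × 0.30 = 0.6 to 0.05 × 0.50 = 2.5 points.
- ABVD: 0.05 × 0.30 = 1.5 to 0.10 × 0.50 = 5.0 points.
- Shift: from 1.5 − 2.5 = −1.0 to 5.0 − 0.6 = +4.4 points.

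The range includes zero even though more ABVD switching was assumed. With equal s and q in both arms, the shift is zero.

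**The case against.** The strongest reply is that the window is deliberate. Both documents tie collection and tabulation to frontline therapy, Protocol 8.1.9 speaks of the safety profile of patients' frontline therapies, and a switch before completion is not an mPFS event either (Protocol 4.1). An all-cause comparison that follows the assigned strategy is legitimate. This stands, and is why the current tables should stay. But the SAP does not say that they describe a strategy, and its objective names the two regimens.

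A reader might infer four stronger claims that the documents do not support:

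- *Every safety output is contaminated.* It is not. Related-event tables exist for all TEAEs, Grade 3 or higher events and SAEs; other tables cover events that modified or stopped study drug; the deaths table does not use this window. For common terms, many switchers may already have been counted before the switch: Grade 3 or higher neutropenia occurred in 17 of 26 patients (65%) given brentuximab vedotin plus AVD in the phase 1 study (Protocol 1.3).
- *Switching will be frequent, or driven by toxicity.* Protocol 6.3.3 and 6.4 permit another frontline regimen only for a Cycle 2 Deauville score of 5, and omitting one agent is not a missed dose. In the phase 1 study, 36 of 37 patients were PET-negative after Cycle 2, though that study was small and had no ABVD-alone control. Table 8-1 would still cover a switch made for any reason.
- *The comparison is biased against ABVD by a known amount.* That rests wholly on assumed unequal switch rates.
- *The laboratory shift tables have the same defect.* SAP 5.11.2 does not say which last dose it means, and the End of Treatment visit is tied to frontline therapy in the Schedule of Events but to study-drug discontinuation in Protocol 7.7. The text does not settle it.

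The exposure mismatch also distorts no planned statistic, since the tables give crude patient incidence.

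Finally, a cut at the switch has its own bias. If the alternative starts on the planned Cycle 3 Day 1 (day 2 × 28 + 1 = 57), the window closes on day 56. That leaves 56 − 43 = 13 days of follow-up instead of 30, and more patients are shortened in the arm with more switching. Protocol 1.5 describes brentuximab vedotin neuropathy as typically cumulative, so later events could be missed. This argues against replacing the main tables, but not against adding a second set.

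**Conclusion.** The point holds for the all-cause TEAE, Grade 3 or higher and SAE tables. They summarise randomized therapy plus any alternative frontline regimen, and nothing planned isolates the regimen comparison named in the objective. Related-event tables mitigate this only in part.

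The consequence for the between-arm comparison is conditional: bias arises only if switch rates or alternative regimens differ by arm. With no switch rate in the documents, neither size nor direction is established. The 0.2 to 8.0 points within an arm and the −1.0 to +4.4 points between arms only show what the assumed inputs would produce. This is a gap in prespecification that is cheap to close, and does not show that the planned safety tables are wrong.

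**What to change.** In SAP 5.11.1 to 5.11.1.2:

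- Keep the frontline-therapy window for the main tables, label them a treatment-strategy summary, and state how switchers are classified by treatment actually received.
- Add prespecified all-cause TEAE, Grade 3 or higher and SAE tables ending at the earlier of 30 days after the last A+AVD or ABVD dose and the day before the first dose of alternative HL therapy.
- Summarise post-switch adverse events separately, by arm and alternative regimen.
- Reconcile exposure reporting between Protocol 8.1.9 and SAP 5.7.2.1 and 5.11. SAP 6 currently records no change from the protocol.

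The cost is one extra set of tables. No new data are needed: details of the alternative regimen are recorded (Protocol 7.4.13) and time of switch is already summarised (SAP 5.7.2.2). In the added tables, follow-up is shorter for switchers and delayed toxicity of the randomized regimen may be missed; those events remain in the main tables. No clinical rule changes.
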